10.3 Other Analysis

Subgroup analyses will be performed for ACI and anterior chamber cells, anterior chamber flare as appropriate by method of assessment (slit lamp versus penlight with handheld magnifying 20 diopter lens), country (region), age group, intraocular lens (IOL) implantation, and iris color.

10.4 Safety Analysis

Safety analyses will be based on the SAF. The SAF will include all subjects who are confirmed to have received the study drug. All subjects in the SAF will be analyzed according to the treatment received.

10.4.1 Treatment Emergent Adverse Events

Adverse events (AEs) are defined in Section 6.1 of the protocol and initiating collection of AEs is defined in Section 5.1.2 of the protocol. Adverse events will be coded using MedDRA dictionary version 13.0.

All AEs collected with start dates following the first administration of study drug or that worsen following the first administration of study drug are considered treatment-emergent adverse events (TEAE).

Adverse events with unknown severity will be counted as severe. Adverse events with unknown relationship to study drug will be counted as related to study drug. Adverse events with partial dates will have their start dates imputed. If the partial date is consistent with the first day of treatment, it will be imputed with this value; otherwise it will be imputed as the earliest possible date consistent with the partial data (first day of month/ year). If a start or end date are completely missing, then the date will be imputed with the dates of the first or last date of treatment, respectively.

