6.3 Reporting Adverse Events and Follow-up

Throughout the course of the study, efforts will be made by the Investigator to remain alert to possible AEs that are either systemic or ocular in nature. The period of observation for collection of AEs extends from the time the subject's parent/legal guardian gives informed consent until the last study visit, Visit 8 (Postoperative Day 90). The first concern will be the safety of the subject, and appropriate medical intervention will be made.

The Investigator or designee will elicit reports of AEs from the subject/subject's parent/legal guardian at each study visit and record all AEs. An assessment of all AEs will be made by the Investigator as to the severity, action taken with study treatment, and causal relationship to study drug.

The terms used to assess the causal relationship of the event to the study drug are:

- **Related:** There is at least a reasonable possibility that the AE/SAE is related to the study drug. Reasonable possibility means that there is evidence to suggest a causal relationship between the drug and the AE.
- **Not Related:** There is little or no reasonable possibility that the AE/SAE is related to the study drug. This assessment implies that the AE/SAE has little or no temporal relationship to the study drug and/or a more likely or certain alternative etiology exists.

When the investigator assesses the AE as “not related” to the study drug, an alternative etiology (ie, concomitant drug, medical history, prior AE, or other source as indicated) must be provided.

The subject’s parent/legal guardian will be instructed to contact the Investigator immediately if any unusual systemic or ocular AEs are noticed between visits.

Additional assessments/visits may be scheduled, as necessary, to ensure the safety of the subject, during the study period. A subject who discontinues due to an AE should be seen for post-study follow-up visits as necessary.

Non-serious AEs that are ongoing upon early discontinuation or at the study exit visit will be followed by the Investigator up to 30 days after the subject exits the study.

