IOP (Goldmann or equivalent) ⁴	X	X	X	X	X	X	X	X
Fundoscopy ⁵		X	X		X			X
Eligibility determination	X	X						
Randomization		X						
AEs ⁶ /Concomitant medications	X	X	X	X	X	X	X	X
Weigh study drug and inspect diaries		X	X	X	X	X		
Dispense study drug and diaries		X ⁷	X	X	X			
Collect study drug and diaries						X		
Exit subject								X

¹ All ophthalmic assessments will be performed bilaterally.

² Visit 2 must occur within 29 days of Visit 1. Screening and surgery cannot take place on the same day.

³ Visit 3 (postoperative day 1) should occur on the next calendar day post-surgery.

⁴ Every effort should be made to obtain slit lamp assessments and the assessment with the 20 dpt magnifying lens and penlight should only be performed if a slit lamp or handheld slit lamp examination cannot be performed. Once one of the methods has been chosen it should be employed throughout the study for each subject. IOP should also be measured with the same method throughout the study for each subject.

⁵ Fundoscopy will be performed bilaterally either at Visit 2 (surgery/randomization) or Visit 3 (postoperative day 1), at Visit 5 (postoperative day 14 ±3 days), and at Visit 8 (postoperative day 90 ±14 days).

⁶ Collection of AEs extends from the time the subject's parent/guardian signs informed consent until the last study visit.

⁷ The subject's parent/legal guardian will be trained with regard to the correct instillation of eye drops without using study drug prior to their administration of the initial dose.

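### SAP 10.4.1 moves missing, or compatible partial, AE start dates to the first treatment day without checking a known end date, so an AE that ended before the first dose can be dated after its own end

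*SAP*

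**What the plan says.** SAP 10.4.1 has three rules for incomplete AE start dates.

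- Partial, and compatible with the first treatment day: "If the partial date is consistent with the first day of treatment, it will be imputed with this value".
- Partial, and not compatible with it: "otherwise it will be imputed as the earliest possible date consistent with the partial data (first day of month/ year").
- Completely missing: "If a start or end date are completely missing, then the date will be imputed with the dates of the first or last date". That is, a missing start becomes the first treatment date and a missing end the last.

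No sentence compares an imputed start with an end date that is known.

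The same section defines treatment-emergent events as "All AEs collected with start dates following the first administration of study drug or that worsen following the first administration of study drug". It does not say whether this is judged by date or by clock time. SAP 6 defines Day 0 as a date, that of randomization and first dose.

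Pre-treatment AEs are in the database. Protocol 6.3 begins: "The period of observation for collection of AEs extends from the time" of consent. Footnote 6 of the SAP visit schedule says the same: "Collection of AEs extends from the time the subject's parent/guardian signs informed consent until the last study visit". Footnote 2 of that schedule allows up to 29 days between screening and surgery and forbids both on one day. SAP 5.1 places the first dose at the end of surgery.

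**The concern.** An AE can start and resolve between consent and surgery. If its start is recorded only to the month or year of surgery, or not at all, the rule moves the start to the day of surgery even when the record shows that the event was already over. The result is an impossible chronology. Depending on how the first-dose day is treated, it can also put an event that the study drug could not have caused into the TEAE tables.

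The outcome turns on the word *following* in the TEAE definition, which leaves the first-dose day open. If that day counts, resolved pre-surgery AEs enter the tables. If it does not, they stay out, but so do AEs whose start was imputed to that day and AEs with a complete Day 0 date, unless they worsen afterwards. Each reading misclassifies some events, and the text does not choose between them. At stake is the accuracy of the TEAE incidence tables.

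**Working it through.** The plan gives no figure on this point to reproduce. The check applies the written rules to test cases and then asks how often the trigger could be met.

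**Step 1. Apply the rules.** The first dose is assumed to be on 20 May 2014. *Inclusive* means a start on or after the first-dose date counts; *strict* means only a later date counts.

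| Recorded start | Known end | Imputed start | TEAE, inclusive | TEAE, strict |
|---|---|---|---|---|
| May 2014 | 12 May | 20 May (8 days after end) | yes | no |
| 2014 | 12 May | 20 May (8 days after end) | yes | no |
| missing | 12 May | 20 May (8 days after end) | yes | no |
| April 2014 | 12 May | 1 April | no | no |
| May 2014 | 30 May | 20 May | yes | no |
| missing | 30 May | 20 May | yes | no |
| 20 May 2014 (complete) | 22 May | not imputed | yes | no |
| June 2014 | 15 June | 1 June | yes | yes |

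The first three rows have a start after the end under either reading, and are false TEAEs only under the inclusive one. The two rows ending 30 May and the complete 20 May row are lost only under the strict one (worsening aside). The April and June rows show that a partial date not compatible with the first treatment day is not moved there.

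**Step 2. Add an end-date check** (imputed start no later than a known end). The three AEs that ended 12 May become non-TEAE under both readings. The two that ended 30 May keep a start of 20 May and are still lost under the strict reading. The end-date check and a first-dose-day rule are therefore both needed.

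**Step 3. How often the trigger could be met.** Assume onset is uniform over a screening interval of L days, with surgery spread evenly over a 30-day month. An onset g days before surgery falls in the same month with probability (30 − g)/30. Averaging over g = 1 to L gives 1 − (L + 1)/60. Counting over all 365 surgery dates of a calendar year gives nearly the same:

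| L (days) | 1 − (L + 1)/60 | Calendar count, same month | Calendar count, same year |
|---|---|---|---|
| 1 | 96.7% | 96.7% | 99.7% |
| 7 | 86.7% | 86.8% | 98.9% |
| 15 | 73.3% | 73.7% | 97.8% |
| 29 | 50.0% | 50.7% | 95.9% |

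These are shares of pre-surgery AEs with month-only (or year-only) start dates that meet the trigger. They are not misclassification rates: a false TEAE also needs a known end date before the first dose and the inclusive reading.

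**Step 4. Effect of one child.** With 140/2 = 70 per arm, one child is 1/70 = 1.4 percentage points of incidence, and only if that child has no other TEAE in the category counted.

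**The case against.** Four points on the other side have force.

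*The definition is event-based.* It refers to an administration, which is an event, so an AE later on Day 0 naturally follows it. Imputing to the first treatment day makes sense only if that day can qualify, and the neighbouring rules are conservative (unknown severity counted as severe, unknown relationship as related). This stands: the SAP does not state a rule that excludes Day 0. A reader might infer that it does, but the text supports only an ambiguity.

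*The two effects exclude each other.* A reader might infer that the SAP both adds resolved pre-surgery AEs and drops same-day ones. It cannot, because each belongs to a different reading. A reader might also infer that every partial start date goes to the first treatment day, but only those compatible with it do.

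*The arms are not treated differently.* Randomization takes place at the end of surgery, so AEs resolved before surgery precede assignment and should add noise to both arms alike. A biased safety comparison is not supported. AEs lost under the strict reading arise at or after assignment, so an equal effect there rests on the rule being identical in both arms and on date completeness not depending on arm, which is reasonable under masking. The TEAE tables in SAP 10.4.1.1 to 10.4.1.3 are descriptive, with no test specified.

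*Data handling limits the numbers.* Protocol 8.3 requires dates on the eCRF and an explanation of omissions, and both it and SAP 2 provide for querying. AEs are also recorded at Visit 2 (Protocol 5.1.2). Such records should be uncommon, but querying does not correct what the rule does with the dates that remain incomplete.

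**Conclusion.** The point holds as a minor defect. Followed exactly, SAP 10.4.1 can give an AE a start later than its own known end. On the reading that the imputation implies, it then counts an AE that ended before the first dose as treatment-emergent. The wording on the first-dose day is a secondary ambiguity: read strictly by date, it would defeat the imputation by removing the events just moved to that day, unless they worsened later.

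The effect on TEAE counts cannot be sized, because the documents do not say how many start dates are partial or missing. The 51% to 97% range rests on the assumption of uniform onset and describes only how often a month-only pre-surgery date would meet the trigger. The primary efficacy analysis is not affected.

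**What to change.** Amend SAP 10.4.1 before database lock:

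1. Impute a missing start, or a partial start compatible with the first treatment day, to that day only if the end date is unknown or falls on or after that day.
2. Never impute a start later than a known end date.
3. Classify an AE known to have ended before the first dose as not treatment-emergent.
4. State that an AE dated on the first-dose day counts as treatment-emergent unless the record shows that it began before the first dose.

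The cost is a few sentences and a small programming change. The downside is in item 4. The first dose comes at the end of surgery, and the documents do not show that AE onset time is collected. Some surgical AEs that began before dosing on Day 0 may therefore be counted, which errs on the conservative side.

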10.4.1.1 Incidence of Treatment-Emergent Adverse Events

Treatment emergent non-ocular AEs will be summarized using discrete summaries at the subject and event level by system organ class and preferred term for each treatment group. Treatment emergent ocular AEs will be summarized for treated study eyes and fellow eyes separately.

10.4.1.2 Relationship of Treatment-Emergent Adverse Events to Study Drug

Treatment emergent AEs will be summarized by relationship to study drug. Relationship of adverse events to study drug may be ‘Not Related’ or ‘Related’. Adverse events that are missing relationship will be presented in the summary table as “Related” but will be presented in the data listing with a missing relationship. Percentages will be calculated out of the number of subjects in the Safety sample.

10.4.1.3 Severity of Treatment-Emergent Adverse Events

A summary of TEAEs by severity will be presented in a table. The severity that will be presented represents the most extreme severity captured. Adverse events will be assessed by the Investigator as “Mild,” “Moderate,” or “Severe.” In the AE severity table, if a subject reported multiple occurrences of the same AE, only the most severe will be presented. Adverse events that are missing severity will be presented on tables as “Severe” but will be presented in the data listing with a missing severity. Percentages will be calculated out of the number of subjects in the Safety sample.

10.4.1.4 Seriousness of Adverse Events

Serious adverse events (SAEs) are defined in Section 6.2 of the protocol. A listing and table of SAEs will be presented.

10.4.1.5 Treatment-Emergent Adverse Events Leading to Discontinuation

All TEAEs resulting in study discontinuation will be presented in a listing.

10.4.1.6 Treatment-Emergent Adverse Events Related to Study Drug

All TEAEs assessed as related to the study drug will be presented with time to onset and outcome in a listing by treatment group.

10.4.1.7 Death

All subject deaths during this study will be collected and presented in a listing. The information presented will include date of death, days on study, cause of death, and relationship of death to study drug.

10.4.2 Surgical Intervention

Surgical procedure data will be presented in a listing.

10.4.3 Other Safety Data

10.4.3.1 Biomicroscopy / Fundoscopy

The slit lamp/penlight with magnifying lens biomicroscopy will be performed at all visits. The biomicroscopy parameters will include:

- Anterior chamber cells or ACI
- Anterior chamber flare or ACI
- Ciliary flush
- Chemosis
- Ocular discharge
- Ocular tearing
- Bulbar conjunctival injection
- Corneal edema
- Hyphema
- Hypopyon
- Posterior synechiae
- Precipitates

Biomicroscopy findings will be summarized at each visit and for the worst case on treatment by subject and parameter. Incidence of treatment-emergent biomicroscopy findings will be tested using the Pearson Chi-squared Test or Fisher's Exact Test as applicable.

The fundoscopy parameters will include:

- Posterior Pole
- Optic Nerve
- Cup/Disc Ratio

Fundoscopy measures will be summarized by visit. Incidence of treatment-emergent fundoscopy findings will be tested using a Pearson Chi-squared Test or Fisher's Exact Test, if applicable.

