5.1.3 Visit 3 (Postoperative Day 1; First Calendar Day after Surgery)

At Visit 3, the following assessments will be performed:

NOTE: All ocular assessments and VA will be performed bilaterally.

- AEs and changes in concomitant medications
- the unmasked designee must weigh both bottles of study drug
- ocular symptoms
- pediatric VA
- biomicroscopy
- IOP measurement

NOTE: Measurement of IOP must occur after the assessment of ocular symptoms, VA and biomicroscopy.

NOTE: If, at any time point after surgery, IOP is elevated, treatment or intervention is left to the Investigator's discretion and the subject is to continue the study.

- fundoscopy, if not performed during surgery

NOTE: Topical antibiotic drops should be administered at least 15 minutes AFTER study drug application.

- review and collect study drug administration diary for compliance. Instruct subject's parent/legal guardian to record time of each instillation on the diary and to bring the diary and study drug (both bottles) to their next visit. Remind subjects that no other information should be recorded in the diary
- dispense new diary
- the unmasked designee must redispense study drug
- instruct subject's parent/legal guardian to continue dosing the study drug QID, at approximately four hour intervals for the next 2 weeks

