Subject's eyes meeting eligibility criteria at both Visit 1 (Screening) and Visit 2 (Surgery/Randomization) were randomized to receive study medication. If both eyes of a subject underwent routine, uncomplicated surgery at Visit 2 (Surgery/Randomization) and met eligibility criteria, the subject's right eye was considered the study eye. In the event that the subject required surgery on the contralateral eye at any time during the study, the fellow eye was treated with standard of care medication.

The subject will receive the first dose of study drug by the unmasked designee at the end of the surgery. Either the unmasked designee or the subject's parent/legal guardian will then administer 1 to 2 drops of study drug to the lower cul-de-sac of the study eye once in the evening on the day of surgery and then 4 times a day (QID), at approximately 4 hour intervals, beginning on the morning after surgery. QID dosing will continue until postoperative day 14, including dosing at appropriate time intervals on the day of a visit. Treatment will be tapered by altering the frequency of study drug dosing to twice a day (BID) during the interval between postoperative days 15 and 21. Treatment will be further tapered to once a day (QD) from postoperative day 22 until day 28, with the last dose being administered on the day prior to Visit 6 (Postoperative Day). No study drug doses were delivered after Visit 6, and subjects returned for post-dosing assessments at Visit 7 (Day 42) and Visit 8 (Day 90). Subjects then exited from the study.²⁸⁾

Schedule of Visits and Parameters

All study tasks should be performed by qualified study site personnel as indicated on the delegation of authority log under the supervision of the Principal Investigator. Furthermore, all ocular signs must be evaluated by an ophthalmologist.

PROCEDURE/ASSESSMENTS ¹	Visit 1 Screening	Visit 2 Surgery/Randomization /Begin Treatment	Visit 3 Follow-up	Visit 4 Follow-up	Visit 5 Follow-up	Visit 6 Follow-up/End Treatment	Visit 7 Follow-up	Visit 8 Study Exit
	Day -15 (±14 days)	Day 0 ²	Day 1 ³	Day 7 (±2 days)	Day 14 (±3 days)	Day 28 (±7 days)	Day 42 (±7 days)	Day 90 (±14 days)
Informed consent, assent (when applicable), and authorization as appropriate for local privacy regulations	X							
Demographic data	X							
Current and relevant medical and ocular history	X							
Ocular symptoms	X		X	X	X	X	X	X
VA assessment	X	X	X	X	X	X	X	X
Slit lamp (biomicroscopy or magnifying lens with penlight) ⁴	X	X	X	X	X	X	X	X

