5.2.3 Safety Endpoints

The safety endpoints include the following:

- Incidence of overall and specific adverse events (AEs)
- Type and incidence of AEs at each visit
- Change in IOP from baseline (Visit 2, Surgery/Randomization) to each visit
- Greatest IOP change from baseline - including the measurement at Visit 3 (Postoperative Day 1)
- Greatest IOP change from baseline - excluding the measurement at Visit 3 (Postoperative Day 1)
- Ocular signs (biomicroscopic examination of the lids, conjunctiva, cornea, anterior chamber without pupil dilation) at each visit

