5.10 Treatment Compliance Follow-up

In order to assess compliance of treatment administration, subject/subject's parent/legal guardian will be instructed to record the date and time of each study drug administration on a diary provided by the Sponsor.

6 General Statistical Considerations

All statistical analyses will be conducted using SAS Version 9.4 or higher.

Continuous data will be summarized using descriptive statistics: n, mean, standard deviation, median, minimum, and maximum. Means and medians will be presented to 1 more decimal place than the recorded data. Standard deviations will be presented to 2 more decimal places than the recorded data. Minimum and maximum values will be presented using the same number of decimal places as the recorded data. Categorical data will be summarized using counts for each category and corresponding percentages. Percentages will be presented to 1 decimal place. Confidence intervals will be presented using the same number of decimal places as the parameter (i.e. mean).

All statistical analyses will generally include summaries by treatment group or by treatment group and scheduled time point, as appropriate.

In general, the baseline value for a variable is defined as the last observation prior to the first dose of double masked study medication (Day 0), including the screening value, if necessary.

Study Day 0 is defined as the date on which a subject was randomized and took the first dose of double masked study medication. Other study days are defined relative to the Study Day 0 as Dose Date – Day 0 date + 1. The visit window for Day 7 is ± 2 , for Day 14 is ± 3 , for Day 28, 42, is ± 7 , and for Day 90 is ± 14 .

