10.1	Change the primary endpoint into ITT with LOCF	Change based on protocol

Section #	Description of Change	Rationale
		amendment 6
10.1	Delete the pattern mixture model part	Change based on protocol amendment 6
10.1	Add “and investigational site as a covariate.”	Site might have significant impact on the primary endpoint.
10.2	Changed Visit 5 to Visit 4, and Day 14 to Day 7	Change based on protocol amendment 6
10.2	Changed Day 29 to Day 28	Change based on protocol amendment 6
10.2	Removed the whole ANCOVA model section	The baseline measurements on Visit 2 (Day 0) were taken prior to the surgery, which means the results should all be negative (no ACI). So it's not meaningful to use baseline as a covariate in this case
10.2	Added “in the study eye” in the second and third bulletins	To clarify that these two tables are only summarized for study eye
10.4.1.1	Added “Treatment-Emergent”	Sponsor requested to clarify
10.4.1.2	Added “Treatment-Emergent”	Sponsor requested to clarify
10.4.1.3	Added “Treatment-Emergent”	Sponsor requested to clarify
10.4.1.5	Added “Treatment-Emergent”	Sponsor requested to clarify
10.4.1.6	Added “Treatment-Emergent”	Sponsor requested to clarify

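### "Treatment-emergent" is undefined for biomicroscopy, and under the SAP's pre-surgical baseline the surgical signs seen on Day 1 count in both arms and dilute the between-arm test for common signs

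*SAP*

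**What the plan says.** - **The test.** SAP 10.4.3.1 lists twelve biomicroscopy parameters. It summarizes them at each visit and as the worst case on treatment, and then says: "Incidence of treatment-emergent biomicroscopy findings will be tested using the Pearson Chi-squared Test" (or Fisher's exact test). It does not say which exam a finding must be new or worse against, and it does not set Visit 3 aside.
- **Baseline.** SAP section 6 says that, in general, "the baseline value for a variable is defined as the last observation prior to the first dose of double masked study medication".
- **First dose.** SAP 5.1: "The subject will receive the first dose of study drug by the unmasked designee at the end of the surgery".
- **Visit 2 exam.** SAP 12.1, giving the reason for a change to section 10.2: "The baseline measurements on Visit 2 (Day 0) were taken prior to the surgery, which means the results should all be negative (no ACI").
- **Treatment-emergent.** The only definition is in SAP 10.4.1, for adverse events: onset or worsening after the first administration of study drug.
- **First exam after dosing.** Visit 3, the first calendar day after surgery, includes biomicroscopy (Protocol 5.1.3).
- **IOP.** SAP 5.2.3 and 10.4.3.3 report the greatest change from baseline including Visit 3, and also "Greatest IOP change from baseline - excluding the measurement at Visit 3 (Postoperative Day 1").

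**The concern.** Surgery falls between the baseline exam and the first exam on treatment. A sign that surgery produces, such as conjunctival injection, chemosis or corneal edema, is therefore absent at baseline and present on Day 1 whichever drug the child receives. On the only reading the SAP supplies, that eye already has a treatment-emergent finding, and nothing later can change its status. The worst case on treatment has a related weakness: nothing keeps a Day 1 grade from setting it.

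Ocular signs are a listed safety endpoint (Protocol 7.1.3, SAP 5.2.3). Signs that appear or remain during the following weeks of steroid are where the two drugs could plausibly differ. If Day 1 signs are frequent, a non-significant result says little about that period but could be read as reassurance.

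**Working it through.** **1. Does Day 1 count?** The order of events is the Visit 2 exam (before surgery), surgery, first dose at the end of surgery, then the Visit 3 exam. With baseline as the last value before the first dose, and the adverse-event meaning of treatment-emergent, a sign absent at Visit 2 and present at Visit 3 counts. This is an inference, because SAP 10.4.3.1 leaves the term open. The protocol does expect some inflammation on Day 1: its rescue section (3.2.3) refers to an anticipated level at Visit 3.

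**2. Which parameters have another between-arm test?** SAP 10.1 and 10.2 compare mean ACI grade (the maximum of cells and flare on slit lamp) at Days 7, 14 and 28. SAP 10.2 also compares ACI grade proportions, synechiae and precipitates at those visits. None of these uses baseline or Day 1. They cover 4 of the 12 parameters (cells/ACI, flare/ACI, synechiae, precipitates). The other 12 − 4 = 8 have only the treatment-emergent test: ciliary flush, chemosis, discharge, tearing, bulbar injection, corneal edema, hyphema and hypopyon.

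**3. The plan's own power figure.** The only one is 98%, for the primary endpoint with 60 per arm, SD 0.47, margin 0.35 and true difference 0. It reproduces: 0.35 / (0.47 × √(2/60)) = 4.079, and 4.079 − 1.960 = 2.119, giving 98.3%. No power is stated for the biomicroscopy test.

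**4. Size of the dilution.** Let d be the share of eyes with the sign on Day 1, equal in both arms, and r the share with the sign at any later exam, taken as independent of d.

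- Incidence including Visit 3: p = d + (1 − d) × r
- Difference between arms: (1 − d) × (r₁ − r₂)

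Inputs: 140 / 2 = 70 per arm (SAP 5.4). Two-sided 5% is assumed, since SAP section 10 states it for efficacy only. Assumed r is 25% versus 5%. The documents give no value for d or r, so d is shown over a range. Power is by exact enumeration.

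| d (Day 1 rate) | Incidence, 25% arm | Incidence, 5% arm | Difference (points) | Fisher power | Chi-squared power |
|---|---|---|---|---|---|
| 0 (Visit 3 excluded) | 25.0% | 5.0% | 20 | 91% | 94% |
| 10% | 32.5% | 14.5% | 18 | 65% | 73% |
| 25% | 43.75% | 28.75% | 15 | 39% | 45% |
| 50% | 62.5% | 52.5% | 10 | 17% | 22% |
| 80% | 85.0% | 81.0% | 4 | 6.5% | 10% |

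Example at d = 50%: 0.50 + 0.50 × 0.25 = 0.625, 0.50 + 0.50 × 0.05 = 0.525, difference 0.10.

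**5. Other assumed rates** (chi-squared approximation, 70 per arm). Later rates of 10% versus 30% give 85% power at d = 0, 66% at 10%, 22% at 50% and 6% at 90%. Later rates of 20% versus 40% give 74%, 60%, 24% and 7%. The pattern does not depend on one choice of rates.

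**The case against.** - **No bias.** Surgery precedes randomization, so Day 1 surgical signs should be balanced between arms. They cost power but do not favor either drug, and no claim or decision rule depends on this test. This stands.
- **Later signs are still reported.** All twelve parameters are summarized by visit and arm, so nothing is hidden. This stands, but those summaries are descriptive; the formal test of the eight parameters is still the diluted one.
- **It is not the only between-arm comparison of ocular signs.** A reader might infer that it is. For ACI (cells and flare), synechiae and precipitates, SAP 10.1 and 10.2 show otherwise.
- **Most children affected, or a test that cannot detect a difference.** A reader might go this far, but no Day 1 rate is documented for any sign. Rates will vary by sign, and hyphema or hypopyon may be uncommon. With the same 25% versus 5%, Fisher power is still 78% at a Day 1 rate of 5%. It approaches the test's nominal level only when Day 1 rates are very high.
- **The worst case as a comparison with the pre-surgical exam.** The SAP does not describe it that way; it simply does not exclude Day 1.
- **SAP 12.1 as proof that all signs are absent at Visit 2.** It speaks of ACI only. It gives that as the reason baseline is uninformative as a covariate, which is not a correction for Day 1 signs.
- **Making Visit 3 the reference for the test.** This is tempting but costly. A sign present on Day 1 that persists unchanged would never be an event, and delayed resolution is one way two anti-inflammatory drugs could differ. Visit 3 is also after randomization and on treatment. The IOP precedent keeps the Visit 2 baseline and leaves out the Visit 3 value.

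**Conclusion.** The point holds as an undefined term with a measurable loss of power. On the SAP's own general definitions, Day 1 surgical signs count as treatment-emergent in both arms. In the illustration, a sign present on Day 1 in a quarter of eyes more than halves the power (91% to 39%), while one present in a tenth leaves 65%. The practical weight falls on the eight parameters with no other between-arm test.

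The size rests on assumed rates, equal Day 1 incidence in the arms, independence of Day 1 and later signs, and a two-sided 5% level. If later signs are mostly Day 1 signs that persist, the independence formula understates the dilution. The finding leaves the primary analysis untouched. It is a low-cost improvement to a safety comparison and does not invalidate it.

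**What to change.** In SAP 10.4.3.1:

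1. State the reference exam for treatment-emergent findings: Visit 2, or screening where Visit 2 is missing, as in section 6. State that the finding must be absent at that exam and present later, or of a higher grade later.
2. Present and test treatment-emergent incidence, and present and test the worst case on treatment, in two versions: including Visit 3 and excluding it. Both keep the Visit 2 baseline, which parallels the two versions of greatest IOP change.
3. If wanted, add worsening relative to Visit 3 as a descriptive table only.

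The data are already collected. The cost is SAP wording, one more set of tables and more unadjusted tests. The version excluding Visit 3 cannot show a drug effect confined to the first day, but the including version still can. Surgical signs that last to Day 7 will still count in the excluding version. That limits the gain in power, but it keeps slow resolution visible.
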